9.6.2.2 Assessment of Safety Topics of Special Interest

AEs that are immune-mediated or potentially immune-mediated will be evaluated separately. These events have been characterized consistently throughout the pembrolizumab clinical development program. Point estimates and 95% CIs for between-group difference is not expected to add value to the safety evaluation, and hence only number and percentage of participants with such pembrolizumab AEOSI will be provided, as well as the number and percentage of participants with corticosteroids administration to treat an AEOSI. Summary statistics will be provided for the analysis of time from first dose to the onset of an AEOSI. Similar approach will be applied to CSAE for lenvatinib.

Table 17 summarizes the analysis strategy for safety endpoints in this study.

Table 17 Analysis Strategy for Safety Parameters

Analysis Part	Safety Endpoint	Descriptive Statistics	95% between-group CI (Graphical display)
Overall Safety Assessment	Specific AEs (incidence ≥10% of participants in one of the treatment groups)	X	X
	Specific Grade 3-5 AE (incidence ≥5% of participants in one of the treatment groups)	X	X
	Specific serious AE (incidence ≥5% of participants in one of the treatment groups)	X	X
	Any AE	X	
	Any Grade 3-5 AE	X	
	Any serious AE	X	
	Any drug-related AE	X	
	Any serious and drug-related AE	X	
	Any Grade 3-5 and drug-related AE	X	
	Discontinuation study treatment due to AE	X	
	AE that resulted in death	X	
	Change from Baseline Results (lab toxicity shift, vital signs)	X	

Analysis Part	Safety Endpoint	Descriptive Statistics	95% between-group CI (Graphical display)
Assessment of safety topics of special interest	Pembrolizumab AEOSI	X	
	Lenvatinib CSAE	X	

AE=adverse event; CI=confidence interval; SAE=serious adverse event; AEOSI=adverse event of special interest; CSAE=clinically significant adverse event; X = results will be provided.

9.6.3 Statistical Methods for Patient-Reported Outcome Analyses

PRO analyses will be performed in Part 2 participants only. Details of PRO analyses will be described in the sSAP.

9.6.4 Summaries of Demographic and Baseline Characteristics

Part 1: The relevant demographics and baseline characteristics will be summarized. The number and percentage of participants screened, randomized, and the primary reasons for screening failure and discontinuation will be displayed.

Part 2: The comparability of the treatment groups for each relevant demographic and baseline characteristic will be assessed by the use of tables and/or graphs. No statistical hypothesis tests will be performed on these characteristics. The number and percentage of participants screened, randomized, and the primary reasons for screening failure and discontinuation will be displayed.

Demographic variables (eg, age), baseline characteristics, primary and secondary diagnoses, and prior and concomitant therapies will be summarized by treatment either by descriptive statistics or categorical tables.

9.7 Interim Analyses

Part 1

In this open-label Safety Run-in Phase, participants will be closely followed for DLTs for 21 days after the first dose of study intervention. If 3 or more DLTs occur in either chemotherapy backbone treatment group during this Safety Run-in, enrollment to Part 2 may be delayed to further examine safety data and consider study design changes.

Part 2

An eDMC will review the unblinded efficacy results and accumulating safety data at planned interim analysis. Treatment-level results of the interim analysis will be provided by the unblinded statistician to the eDMC. The eDMC responsibilities and review schedules will be outlined in the DMC Charter. The recommendations of the eDMC will be communicated to the EOC. If the eDMC recommends modifications to the design of the protocol or

discontinuation of the study, the EOC, and possibly other limited numbers of additional Sponsor personnel, may be unblinded to results at the treatment level to act on these recommendations. Participant-level unblinding to support regulatory filing, should this occur before the end of the study, will be restricted to a designated Sponsor team, who will have no other responsibilities associated with the study. The extent to which individuals are unblinded with respect to the results will be documented.

Additional logistical details, revisions to the above plan, and data monitoring guidance will be provided in the eDMC Charter.

Prior to final study unblinding, the unblinded statistician will not be involved in any discussions regarding modifications to the protocol, statistical methods, identification of protocol deviations, or data validation efforts after the interim analysis.

9.7.1 Efficacy Interim Analysis

One interim analysis is planned in addition to the final analysis for this study. For the interim and final analyses, all randomized participants will be included. Results of the interim analysis will be reviewed by the eDMC. The timing and the purpose of the interim and final analyses are summarized in Table 18. Type I error control for the efficacy analyses as well as efficacy bounds are described in Section 9.8.

Table 18	Summary of	Interim and Fina	ıl Analyses	Strategy for Efficacy

Analyses	Timing	Estimated Time after First Participant Randomized	Primary Purpose of Analysis
IA	Both ~494 PFS events have occurred in CPS ≥1 participants and ~8 months after the last participant randomized. Approximately, 450 OS events in CPS ≥1 participants are expected with this trigger.		Efficacy analysis for ORR, PFS and OS in CPS ≥1 and all participants. This is the final analysis of ORR and PFS, and the IA of OS.
Final Analysis	Both ~537 deaths have occurred in CPS ≥1 participants and ~18 months after the last participant randomized.		Efficacy analysis for OS in CPS ≥1 and all participants. This is the final analysis of OS.

IA=interim analysis; CPS=combined positive score; ORR=objective response rate; OS=overall survival; PFS=progression-free survival

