9.7.2 Safety Interim Analysis

In Part 2, the eDMC will be responsible for periodic interim safety reviews, as specified in the DMC Charter. Interim safety analysis will also be performed at the time of interim

MK-7902-015-08 FINAL PROTOCOL 10-JUN-2025

Confidential

Note for IA and FA: if the events accrue slower than expected, the Sponsor may conduct the analysis with up to 3 additional months of follow-up than the follow-up as described above, or when the specified number of events is observed, whichever occurs first.

efficacy analysis. In this open-label study, participants will be actively monitored at ongoing basis. Because there is limited experience in the full combination of pembrolizumab with lenvatinib and CAPOX or mFOLFOX6, there will be an independent first safety review by an eDMC after at least 20 participants in the experimental arm have completed 2 cycles of induction therapy.

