9.8.1 OS Hypotheses

Figure 7 shows that initial alpha=0.018 will be allocated to the OS hypothesis in CPS ≥1 participants (H1) and no initial alpha will be allocated the OS hypothesis in all participants (H3). According to Figure 7, H1 may also be tested at alpha=0.023999 (H2 and H4 rejected), 0.019001 (H2, H5, and H6 rejected), and 0.025 (H2, H5, H4, and H6 rejected). As an example, Table 19 shows the bounds and boundary properties for H1, when tested at initial alpha=0.018 and full alpha=0.025, derived using a Lan-DeMets O'Brien-Fleming spending function based on the predicted number of events, at the planned time of analysis.

The bounds provided in Table 19 are based on the assumption that the expected events at IA and FA are 450 and 537 in CPS ≥1 participants, respectively. At the time of an analysis, the observed number of events may differ substantially from the expected. To avoid overspending at the IA and leave reasonable alpha for the final analysis, the minimum alpha spending strategy will be adopted. At the IA, the information fraction used in Lan-DeMets spending function to determine the alpha spending at the IA will be based on the minimum of the expected information fraction and the actual information fraction at each analysis. Specifically,

MK-7902-015-08 FINAL PROTOCOL 10-JUN-2025

Confidential

In the scenario that the events accrue slower than expected and the observed number of events is less than the expected events at a given analysis, the information fraction will be calculated as the observed number of events at the IA over the target number of events at FA.

In the scenario that the events accrue faster than expected and the observed number of events exceed the expected number of events at a given analysis, then the information fraction will be calculated as the expected number of events at the IA over the target number of events at FA. For example, at IA, if 470 OS events have occurred (ie, more than the expected 450 OS events), the alpha spending at IA will be according to the expected information fraction (450/537 = 84%) instead of the actual information fraction (470/537 = 88%).

The final analysis timing is driven by OS events from the CPS ≥ 1 participants. The final analysis will use the remaining Type I error that has not been spent at the IA. The event counts for all analyses will be used to compute correlations.

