9.9 Sample Size and Power Calculations

The enrollment is complete.

Part 1

Approximately 12 subjects will be enrolled in Part 1. The sample size is determined based on clinical considerations to rule out dose-limiting toxicities.

Part 2

The study will randomize participants in a 1:1 ratio into the experimental group and the control group. PFS and OS are primary endpoints for the study, with ORR as the key secondary endpoint. Approximately 878 participants are planned to be enrolled. The actual overall sample size of the study for all participants is 880. The sample size for CPS ≥1 participants is approximately 680. Power and IA calculations were performed using the gsDesign R package.

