9.9.1 Overall Survival

There will be \sim 537 deaths at the OS final analysis in CPS \geq 1 participants. With 537 deaths, the study has \sim 85% power for detecting an HR of 0.76 at an initially assigned 0.018 (one-sided) significance level.

If H1 (ie, OS endpoint in CPS \geq 1 participants) is rejected, alpha=0.018 can be passed from H1 to H3 (OS endpoint in all participants). There will be ~701 deaths in all participants at the final OS analysis. With 701 deaths, the study has ~80% power for detecting an HR of 0.80 at a significance level of 0.018 (1-sided).

The sample size (number of participants) calculations are based on the following assumptions: (1) the actual enrollment period is 22 months, and the ramp-up period of enrollment is 6 months; (2) the duration of OS follow exponential distribution; (3) median OS is 11.5 months in the control group and the true HR are 0.76 in CPS ≥ 1 participants and 0.80 in all participants; (4) the annual dropout rate is 1% for OS endpoint. The median OS in the control group is based on CPS ≥ 1 participants treated with the standard care of chemotherapy from KN062 (the first line of HER-2 negative, previously untreated, unresectable or metastatic gastric/GEJ adenocarcinoma).

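### Do the stated analysis months (31 and 41) contradict the stated event counts under the plan's own assumptions?

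*Combined protocol and SAP*

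**What the plan says.** Table 18 (section 9.7.1) sets the interim trigger as "Both ~494 PFS events have occurred in CPS ≥1 participants and ~8 months after the last participant randomized" and adds: "Approximately, 450 OS events in CPS ≥1 participants are expected with this trigger". The final analysis follows when "Both ~537 deaths have occurred in CPS ≥1 participants and ~18 months after the last participant randomized". The note to the table provides that, if events come slowly, "the Sponsor may conduct the analysis with up to 3 additional months of follow-up than the follow-up as described above", or analyze once the count is reached if that is earlier.

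Tables 19 to 22 (sections 9.8.1 and 9.8.2) put 450 OS events (CPS ≥1), 588 OS events (all participants), 494 PFS events (CPS ≥1) and 644 PFS events (all) at month 31. They put 537 and 701 deaths at month 41.

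On accrual, section 9.9 says "The enrollment is complete" and gives the actual overall size as 880. Section 9.9.1 says "the actual enrollment period is 22 months, and the ramp-up period of enrollment is 6 months". It also states that OS is exponential and that "median OS is 11.5 months in the control group", with hazard ratios of 0.76 (CPS ≥1) and 0.80 (all) and 1% annual dropout. Section 9.9.2 gives the PFS inputs: control median 6 months, hazard ratios 0.70 and 0.73, 25% annual dropout. Neither section states the enrollment rate after the ramp-up.

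**The concern.** Section 9.9 seems to give everything needed to project event dates. The natural default is a ramp-up followed by a constant rate, and that projection reaches every count later than the tables say, by roughly three months. Dropping the ramp altogether leaves the dates 1.4 to 2.2 months late, so the ramp-up seems to make the mismatch worse whatever its shape.

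The follow-up times in Table 18 matter because the 3-month allowance is measured from them. Counted from 8 and 18 months after a 22-month enrollment, the allowance ends at months 22 + 8 + 3 = 33 and 22 + 18 + 3 = 43. If the counts were really expected at about months 34 and 44, a provision meant for slow events could apply when events arrive exactly as planned, and the interim analysis, which is also the final analysis of PFS and ORR, could be run slightly short of its counts.

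**Working it through.** **1. Bounds and power.** With 450/537 events, one-sided alpha 0.018 and Lan-DeMets O'Brien-Fleming spending, a two-look calculation gives Z bounds of 2.335 and 2.165 (Table 19: 2.335 and 2.166). Power at HR 0.76 is 0.7175 and 0.8536 (Table 19: 0.7182 and 0.8541). With 588/701 events and HR 0.80 it gives 0.6448 and 0.7960 (Table 20: 0.6452 and 0.7969). The counts and the power agree; only the calendar is in question.

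**2. Projection formula.** Expected events at month T are the sum over the two arms of (N/2) × the average over entry times u of [λ/(λ+η)] × [1 − exp(−(λ+η)(T−u))]. N is 680 for CPS ≥1 and 880 for all participants.

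- OS control: λ = ln 2/11.5 = 0.06027 per month. Experimental, CPS ≥1: 0.76 × 0.06027 = 0.04581. Dropout: η = −ln(0.99)/12 = 0.00084.
- PFS control: λ = ln 2/6 = 0.11552. Experimental, CPS ≥1: 0.70 × 0.11552 = 0.08087. Dropout: η = −ln(0.75)/12 = 0.02397.

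**3. How early entry must be.** Expected events are concave in entry time, so the mean entry time limits what any curve can yield. Reaching 450 OS events by month 31 needs a mean entry no later than month 10.1. Reaching 537 deaths by month 41 needs one no later than month 10.5.

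- Flat accrual: mean 22/2 = 11.0, too late.
- Linear 6-month ramp, then constant: (12 + 224)/(3 + 16) = 236/19 = 12.4, too late.
- Linear 6-month ramp, full rate to month 14, then 20% of full rate to month 22: (12 + 80 + 28.8)/(3 + 8 + 1.6) = 120.8/12.6 = 9.6, early enough.

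In each fraction the denominator is the area under the rate curve, piece by piece, and the numerator is the same integral weighted by time. So the shape after the ramp decides the matter. A ramp-up makes mean entry later than 11.0 only if the rate never falls afterwards.

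**4. Projected counts by accrual curve (all over 22 months).** Taper A is the third curve in step 3. Taper B has the same ramp, full rate to month 16 and a 10% tail. Taper C has the same ramp and then a linear decline to 10% at month 22.

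| Count (stated) | Flat | Ramp, then constant | Taper A | Taper B | Taper C |
|---|---|---|---|---|---|
| OS, CPS ≥1, month 31 (450) | 425.6 | 409.9 | 448.9 | 447.2 | 445.0 |
| OS, all, month 31 (588) | 558.7 | 538.2 | 589.0 | 586.8 | 583.9 |
| PFS, CPS ≥1, month 31 (494) | 479.0 | 471.6 | 494.6 | 494.6 | 492.1 |
| PFS, all, month 31 (644) | 625.5 | 616.0 | 645.5 | 645.6 | 642.4 |
| Deaths, CPS ≥1, month 41 (537) | 525.4 | 516.2 | 539.0 | 538.0 | 536.7 |
| Deaths, all, month 41 (701) | 687.6 | 675.8 | 705.1 | 703.8 | 702.1 |

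The first two columns are the apparent error: 450 OS events fall at month 33.0 (flat) or 34.2 (ramp, then constant), and 537 deaths at 42.6 or 43.8. Taper A meets all six stated counts; its largest deviation is 705.1/701 − 1 = 0.6%. The largest deviation of B or C is 445.0/450 − 1 = −1.1%. In taper A, 11/12.6 = 87% of participants have entered by month 14, an ordinary rise, plateau and tail that keeps the stated 6-month ramp-up.

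**5. The follow-up times.** Table 18 requires both the event count and the follow-up, so the later of the two governs. The 8 and 18 months are minimum follow-up, not forecasts of when the counts arrive. A minimum that is met before the events does not contradict them. Months 22 + 8 = 30 and 22 + 18 = 40 differ from the tables' 31 and 41 by one month, and the follow-up times are given as approximate.

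**6. The 3-month limit.** At months 33 and 43, ramp-then-constant accrual gives 436 of 450 OS events, 487 of 494 PFS events and 531 of 537 deaths. Interim OS power would be about 69% instead of 72%, and final OS power 85.1% against 85.4%. Under taper A the same dates give 471 OS events and 552 deaths, so there is no shortfall.

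**The case for a change.** The tapering curves were chosen to test whether the stated figures can be reached; the plan prints none of them. A reader working only from section 9.9 would reasonably assume a constant rate after the ramp, and would then be unable to reproduce the months. That stands: the post-ramp accrual is missing detail, and the months cannot be verified from the text alone. It does not make them wrong. Section 9.9 reports the realized enrollment period and the realized sample size, so it is plausible that the projections used the realized accrual as well, although the plan does not say so.

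Setting the tables to about months 34 and 44 could therefore replace correct figures. Moving Table 18 to about 12 and 22 months after last randomization would not be an editorial change either. It would raise the minimum follow-up and could delay both analyses beyond the point where their event counts are met.

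Section 9.9.1 bases its 11.5-month control median on KN062, for which section 2.2.2.1 reports 11.1 months. This is a separate, minor point. Using 11.1 moves 450 OS events only to month 33.5 with the ramp then constant (32.3 flat), so it neither creates nor settles the question.

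**Conclusion.** The concern does not hold. Under the stated medians, hazard ratios, dropout rates and 22-month enrollment with a 6-month ramp-up, the stated counts and months are mutually compatible: one plain ramp, plateau and tail reproduces all six to within 0.6%. The gap of about three months comes from assuming that accrual stayed constant after the ramp, which the plan does not say. This conclusion converts annual dropout d to a monthly hazard as −ln(1−d)/12 and assumes the same accrual curve for CPS ≥1 and all participants. It shows that the figures are attainable, not which curve the sponsor used.

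If accrual had in fact been constant after the ramp, the cost would still be small. The triggers wait for events, and the 3-month provision permits an earlier analysis without requiring it. Section 9.8.1 limits interim alpha spending when fewer events are observed. In that case, at the 3-month limit, final OS power would fall by 85.4 − 85.1 = 0.3 percentage points and interim OS power by about 3, with type I error essentially unaffected.

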9.7.2 Safety Interim Analysis

In Part 2, the eDMC will be responsible for periodic interim safety reviews, as specified in the DMC Charter. Interim safety analysis will also be performed at the time of interim

MK-7902-015-08 FINAL PROTOCOL 10-JUN-2025

Confidential

Note for IA and FA: if the events accrue slower than expected, the Sponsor may conduct the analysis with up to 3 additional months of follow-up than the follow-up as described above, or when the specified number of events is observed, whichever occurs first.

efficacy analysis. In this open-label study, participants will be actively monitored at ongoing basis. Because there is limited experience in the full combination of pembrolizumab with lenvatinib and CAPOX or mFOLFOX6, there will be an independent first safety review by an eDMC after at least 20 participants in the experimental arm have completed 2 cycles of induction therapy.

9.8 Multiplicity

Part 1

No multiplicity adjustment is needed because there is no hypothesis testing.

Part 2

The study uses an extension of the graphical method of Maurer and Bretz [Maurer, W. and Bretz, F. 2013] to provide strong multiplicity control for multiple hypotheses while making the interim and final analysis timing more flexible. According to the Maurer and Bretz approach, study hypotheses may be tested in a group sequential fashion, and when a particular null hypothesis is rejected, the alpha allocated to that hypothesis can be reallocated to other hypothesis tests. Figure 7 shows the initial 1-sided alpha allocation for each hypothesis in the ellipse representing the hypothesis. The weights for reallocation from each hypothesis to the others are represented in the boxes on the lines connecting hypotheses.

[figure not shown]

Figure 7 Multiplicity Graph for Type I Error Control of Study Hypotheses

CPS=combined positive score; ORR=objective response rate; OS=overall survival; PFS=progression-free survival

The extended graphical method spends alpha as a function of the minimum of the actual event information fraction and the expected event information fraction. This ensures that the actual spending will be no more aggressive than the planned spending while at the same time ensuring that not all alpha is spent prior to final planned event counts.

9.8.1 OS Hypotheses

Figure 7 shows that initial alpha=0.018 will be allocated to the OS hypothesis in CPS ≥1 participants (H1) and no initial alpha will be allocated the OS hypothesis in all participants (H3). According to Figure 7, H1 may also be tested at alpha=0.023999 (H2 and H4 rejected), 0.019001 (H2, H5, and H6 rejected), and 0.025 (H2, H5, H4, and H6 rejected). As an example, Table 19 shows the bounds and boundary properties for H1, when tested at initial alpha=0.018 and full alpha=0.025, derived using a Lan-DeMets O'Brien-Fleming spending function based on the predicted number of events, at the planned time of analysis.

The bounds provided in Table 19 are based on the assumption that the expected events at IA and FA are 450 and 537 in CPS ≥1 participants, respectively. At the time of an analysis, the observed number of events may differ substantially from the expected. To avoid overspending at the IA and leave reasonable alpha for the final analysis, the minimum alpha spending strategy will be adopted. At the IA, the information fraction used in Lan-DeMets spending function to determine the alpha spending at the IA will be based on the minimum of the expected information fraction and the actual information fraction at each analysis. Specifically,

MK-7902-015-08 FINAL PROTOCOL 10-JUN-2025

Confidential

In the scenario that the events accrue slower than expected and the observed number of events is less than the expected events at a given analysis, the information fraction will be calculated as the observed number of events at the IA over the target number of events at FA.

In the scenario that the events accrue faster than expected and the observed number of events exceed the expected number of events at a given analysis, then the information fraction will be calculated as the expected number of events at the IA over the target number of events at FA. For example, at IA, if 470 OS events have occurred (ie, more than the expected 450 OS events), the alpha spending at IA will be according to the expected information fraction (450/537 = 84%) instead of the actual information fraction (470/537 = 88%).

The final analysis timing is driven by OS events from the CPS ≥ 1 participants. The final analysis will use the remaining Type I error that has not been spent at the IA. The event counts for all analyses will be used to compute correlations.

Of note, while the information fraction used for alpha spending calculation will be the minimum of the actual information fraction and the expected information fraction, the correlations required for deriving the bounds will still be computed using the actual information fraction based on the observed number of events at each analysis over the target number of events at FA.

The minimum spending approach assumes timing is not based on any observed Z-value and thus the Z test statistics used for testing conditioned on timing are multivariate normal. Given the probabilities derived with the proposed spending method, the correlations based on actual event counts are used to compute bounds that control the Type I error at the specified alpha level for a given hypothesis conditioned on the IA timing. Because this is true regardless of what is conditioned on, the overall Type I error for a given hypothesis unconditionally is controlled at the specified level. By using more conservative spending early in the study, power can be retained to detect situations where the treatment effect may be delayed.

Table 19 Efficacy Boundaries and Properties for OS Analysis in CPS ≥1 Participants

Analysis	Value	α=0.018	α=0.025
IA: 84% ^a	Z	2.3350	2.1880
N: 680	p (1-sided) ^b	0.0098	0.0143
Events: 450	HR at bound	0.8022	0.8135
Month: 31	P(Cross) if HR=1 ^d	0.0098	0.0143
	P(Cross) if HR=0.76°	0.7182	0.7657
Final	Z	2.1660	2.0360
N: 680	p (1-sided) ^b	0.0152	0.0209
Events: 537	HR at bound	0.8294	0.8388
Month: 41	P(Cross) if HR=1 ^d	0.0180	0.0250
	P(Cross) if HR=0.76°	0.8541	0.8825

CPS=combined positive score; HR=hazard ratio; IA=interim analysis

- a Percentage of expected number of events at the IA over the expected number at final analysis.
- b Nominal alpha for group sequential testing.
- c HR at bound is the approximate HR required to reach an efficacy bound.
- d Probability of crossing a bound under the null hypothesis.
- e Probability of crossing a bound under the alternative hypothesis.

OS hypothesis in all participants (H3) does not have initial alpha assignment but may receive alpha stepped down from OS hypothesis in CPS ≥1 participants (H1). H3 may be tested at alpha= 0.018 (H1 rejected), 0.023999 (H1, H2, and H4 rejected), 0.019001 (H1, H2, H5, and H6 rejected), and 0.025 (H1, H2, H5, H4, and H6 rejected). As an example, Table 20 shows the bounds and boundary properties for H3, when tested at alpha=0.018 and full alpha=0.025, derived using a Lan-DeMets O'Brien-Fleming spending function based on the predicted number of events at the planned time of analysis.

Table 20	Efficacy E	Boundaries and	Properties f	or OS Anal	ysis in All Participants

Analysis	Value	α=0.018	α=0.025
IA: 84% ^a	Z	2.3350	2.1870
N: 880	p (1-sided) ^b	0.0098	0.0144
Events: 588	HR at bound ^c	0.8247	0.8349
Month: 31	P(Cross) if HR=1 ^d	0.0098	0.0144
	P(Cross) if HR=0.80 ^e	0.6452	0.6984
Final	Z	2.1660	2.0360
N: 880	p (1-sided) ^b	0.0152	0.0209
Events: 701	HR at bound c	0.8491	0.8575
Month: 41	P(Cross) if HR=1 ^d	0.0180	0.0250
	P(Cross) if HR=0.80 ^e	0.7969	0.8326

HR=hazard ratio; IA=interim analysis; OS=overall survival.

- a Percentage of expected number of events at the IA over the expected number at final analysis.
- b Nominal alpha for group sequential testing.
- c HR at bound is the approximate HR required to reach an efficacy bound.
- d Probability of crossing a bound under the null hypothesis.
- e Probability of crossing a bound under the alternative hypothesis.

